### Toxicology

- Hematological changes attributable to the pharmacological effect of NS-018 were observed in a 4-week repeated-dose oral toxicity study in rats. Those changes were almost recovered at the end of the 4-week recovery period. One animal in the 150 mg/kg group died.

- Hematological, renal and gastrointestinal tract changes were also observed in a 4-week repeated-dose oral toxicity study in dogs. All 6 animals in the 150 mg/kg group died.
- In the 4-week repeated-dose studies, the maximum tolerated dose (MTD) of NS-018 was 50 mg/kg/day in both rats and dogs. No observed adverse effect level (NOAEL) was determined to be 15mg/kg/day in male rats. The severely toxic dose in 10% of rats (STD10 of rats) was 150 mg/kg and the highest non-severely toxic dose (HNSTD) in dogs was 50 mg/kg/day.
- In the 13-week repeated dose studies, the MTD of NS-018 was 30 mg/kg/day in rats and 50 mg/kg/day in dogs, respectively. NOAEL was not determined in both rats and dogs.
- NS-018 did not induce gene mutations.
- NS-018 induced numerical aberration in the *in vitro* chromosomal aberration test. On the contrary, NS-018 did not induce structural chromosome aberration.
- NS-018 increased the incidence of micronucleated immature erythrocytes in the *in vivo* micronucleus assay in rats, whereas NS-018 did not cause deoxyribonucleic acid (DNA) damage in the liver or peripheral blood cells in the rat comet (single-cell gel electrophoresis) assay.
- NS-018 did not induce phototoxic response in the *in vitro* 3T3 NRU photo toxicity test.

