**8.1.2 Definition of Adverse Events**

An AE is any untoward medical occurrence that occurs in a patient or clinical investigation subject administered a pharmaceutical product, and which does not necessarily have to have a causal relationship with this treatment. An AE can therefore be any unfavorable and unintended sign (including abnormal laboratory finding), symptom, or disease temporally associated with the use of an investigational product, whether or not considered related to the product.

Progression of disease is considered an efficacy outcome parameter and should not be captured as an AE.

All AEs, including intercurrent illnesses, occurring during the study will be documented in the eCRF. Concomitant illnesses, which existed before entry into the study, will not be considered AEs unless they worsen during the treatment period. All AEs, regardless of the source of identification (e.g., physical examination, laboratory assessment, ECG, reported by patient), must be documented.

Pre-existing conditions will be recorded in the eCRF on the Medical History or appropriate page.

A treatment-emergent AE (TEAE) will be defined as an AE that begins or that worsens in severity after at least one dose of study drug has been administered.

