#### 8.1.3.1 Seriousness

A serious AE (SAE) is defined as an AE that meets **any** of the following criteria:

- Results in death;
- Is life-threatening;

NOTE: The term “life-threatening” in the definition of “serious” refers to an event in which the patient was at risk of death at the time of the event. It does not refer to an event, which hypothetically might have caused death, if it were more severe.

- Requires hospitalization or prolongation of existing hospitalization;  
NOTE: In general, hospitalization for treatment of a pre-existing condition(s) that did not worsen from baseline is not considered an AE and should not be reported as an SAE.
- Results in disability/incapacity;
- Is a congenital anomaly/birth defect; or
- Is an important medical event.

NOTE: Important medical events that may not result in death, be life-threatening, or require hospitalization may be considered SAEs when, based upon appropriate medical judgment, they may jeopardize the patient and may require medical or surgical intervention to prevent one of the outcomes listed above. Examples of such medical events include allergic bronchospasm requiring intensive treatment in an emergency room or at home, blood dyscrasias or convulsions that do not result in inpatient hospitalizations, or the development of drug dependency.

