#### 8.1.3.2 Intensity

Investigators should assess the severity of AEs according to CTCAE (see Appendix H). In general, CTCAE v4.0 Severity Grades are:

Grade 1:	Mild; asymptomatic or mild symptoms; clinical or diagnostic observations only; intervention not indicated;
Grade 2:	Moderate; minimal, local or noninvasive intervention indicated;
Grade 3:	Severe or medically significant but not immediately life-threatening; hospitalization or prolongation of hospitalization indicated; disabling; limiting self-care;
Grade 4:	Life-threatening consequences; urgent intervention indicated;
Grade 5:	Death related to AE.

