## **8.2 Serious Adverse Event Reporting - Procedure for Investigators**

### **Initial Reports**

All SAEs occurring from the time of the administration of the first dose of study drug until 30 days following the last administration of study drug must be reported to PAREXEL **within 24 hours** of the knowledge of the occurrence (this refers to any AE that meets any of the aforementioned serious criteria). Serious AEs that the investigator considers related to study drug occurring after the 30-day follow-up period will also be reported to PAREXEL. Events that occur after signing consent that are considered related to a required study procedure will also be captured as AEs/SAEs.

To report the SAE, fax the completed SAE report form to PAREXEL (fax number listed below) within 24 hours of awareness. PAREXEL safety personnel are available for SAE reporting on a 24-hour basis. Reports are reviewed during normal business hours.

Safety Contact Information:  
PAREXEL International  
[name]  
[name]

SAE Contact Information:

PPD

Serious AEs should be reported to the reviewing Institutional Review Board (IRB) according to individual requirements. A copy of that report must be retained at the investigative site and filed in the investigator Site File.

The sponsor will notify FDA and all participating investigators in an IND safety report of any adverse experience associated with the use of the drug that is both serious and unexpected or of potentially serious risks from clinical trials or any other source, as soon as possible, but no later than 15 calendar days after the

sponsor receives the safety information and determines that the information qualifies for reporting.

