**12.4 Efficacy Analyses**

Since the primary objective of this study is to evaluate the safety, tolerability, MTD, and clinically active dose of NS-018 in patients with PMF, post-PV MF, or post-ET MF, no formal hypothesis testing will be performed for efficacy parameters. Efficacy analysis will be based on the Efficacy Population.

The responses to treatment assessed using the IWG consensus criteria(Phase I) and the IWG MRT and ELN Response Criteria (Phase II)will be tabulated by dose level and visit. The number and percentage of patients achieving the response will be provided for each response level. The objective response rate (the percentage of patients with confirmed complete remission (CR), partial response (PR), or clinical improvement (CI) during the treatment period) and its 95% exact binomial confidence interval will be provided by dose level. Quality of life assessed using the MF SAF (Phase I) or MPN SAF (MPN-10) (Phase II) will be summarized by dose level and visit. Change in spleen size by MRI (CT scan for patients not able to tolerate MRI) for the Phase 2 portion will be summarized for the cohort.

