3. Clinical improvement (CI)	
Requires one of the following in the absence of both disease progression (as outlined below) and CR/PR assignment (CI response is validated only if it lasts for no fewer than 8 weeks)
 
(1) A minimum 2 -g/L increase in hemoglobin level or becoming transfusion independent (applicable only for patients with baseline hemoglobin level of less than 100 g/L).‡
 
(2) Either a minimum 50% reduction in palpable splenomegaly of a spleen that is at least 10 cm at baseline or a spleen that is palpable at more than 5 cm at baseline becomes not palpable.§
 
(3) A minimum 100% increase in platelet count and an absolute platelet count of at least <math>50,000 \times 10^9/L</math> (applicable only for patients with baseline platelet count below <math>50 \times 10^9/L</math>).
 
(4) A minimum 100% increase in ANC and an ANC of at least <math>0.5 \times 10^9/L</math> (applicable only for patients with baseline absolute neutrophil count below <math>1 \times 10^9/L</math>).

4. Progressive disease (PD)	Requires one of the following: 
	(1) Progressive splenomegaly that is defined by the appearance of a previously absent splenomegaly that is palpable at greater than 5 cm below the left costal margin or a minimum 100% increase in palpable distance for baseline splenomegaly of 5-10 cm or a minimum 50% increase in palpable distance for baseline splenomegaly of greater than 10 cm.
	(2) Leukemic transformation confirmed by a bone marrow blast count of at least 20%.
	(3) An increase in peripheral blood blast percentage of at least 20% that lasts for at least 8 weeks.
5. Stable disease (SD)	None of the above.
6. Relapse	Loss of CR, PR, or CI. In other words, a patient with CR or PR is considered to have undergone relapse when he or she no longer fulfills the criteria for even CI. However, changes from either CR to PR or CR/PR to CI should be documented and reported.

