Anemia response	
Transfusion-independent patients: a <math>\geq 20</math> g/L increase in hemoglobin level  
 
Transfusion-dependent patients: becoming transfusion-independent{

Spleen response#	A baseline splenomegaly that is palpable at 5-10 cm, below the LCM, becomes not palpable   or
	A baseline splenomegaly that is palpable at $>10$ cm, below the LCM, decreases by $\geq 50\%**$
	A baseline splenomegaly that is palpable at $<5$ cm, below the LCM, is not eligible for spleen response
	A spleen response requires confirmation by MRI or computed tomography showing $\geq 35\%$ spleen volume reduction
Symptoms response	A $\geq 50\%$ reduction in the MPN-SAF TSS††

Progressive disease ‡‡	Appearance of a new splenomegaly that is palpable at least 5 cm below the LCM or
	A $\geq 100\%$ increase in palpable distance, below LCM, for baseline splenomegaly of 5-10 cm or
	A 50% increase in palpable distance, below LCM, for baseline splenomegaly of $>10$ cm or
	Leukemic transformation confirmed by a bone marrow blast count of $>20\%$ or A peripheral blood blast content of $\geq 20\%$ associated with an absolute blast count of $\geq 1 \times 10^9/L$ that lasts for at least 2 weeks
Stable disease	Belonging to none of the above listed response categories
Relapse	No longer meeting criteria for at least CI after achieving CR, PR, or CI, or
	Loss of anemia response persisting for at least 1 month or
	Loss of spleen response persisting for at least 1 month
Recommendations for assessing treatment-induced cytogenetic and molecular changes	
Cytogenetic remission	At least 10 metaphases must be analyzed for cytogenetic response evaluation and
	requires confirmation by repeat testing within 6 months window
	CR: eradication of a preexisting abnormality
	PR: $\geq 50\%$ reduction in abnormal metaphases (partial response applies only to patients with at least ten abnormal metaphases at baseline)
Molecular remission	Molecular response evaluation must be analyzed in peripheral blood granulocytes and
	requires confirmation by repeat testing within 6 months window
	CR: Eradication of a pre-existing abnormality
	PR: $\geq 50\%$ decrease in allele burden (partial response applies only to patients with at least 20% mutant allele burden at baseline)
Cytogenetic/molecular relapse	Re-emergence of a pre-existing cytogenetic or molecular abnormality that is confirmed by repeat testing

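### Leukemic transformations and deaths attributed only to progression get no causality assessment, SAE report or line in the planned safety event outputs

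*Combined protocol and SAP*

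**What the plan says.** Section 8.1.2 begins with a broad AE definition that covers any unfavorable sign, symptom or disease arising in time with the product, related or not. It then removes one class of event: "Progression of disease is considered an efficacy outcome parameter and should not be captured as an AE". No exception is given for fatal progression or for leukemia.

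Both sets of response criteria place leukemia inside that class. Appendix I (Phase 1) lists under progressive disease "Leukemic transformation confirmed by a bone marrow blast count of at least 20" percent. Appendix K (Phase 2) lists under the same heading "Leukemic transformation confirmed by a bone marrow blast count of" more than 20 percent. Each appendix also has a progression criterion based on peripheral blasts.

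Seriousness depends on AE status. Under Section 8.1.3.1 a serious AE "is defined as an AE that meets" one of the listed criteria. Section 8.1.3.2 describes Grade 5 as "Death related to AE". The 24-hour reporting duty in Section 8.2 carries the gloss "this refers to any AE that meets any of the aforementioned serious criteria".

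The events planned for output in Section 12.5 are all AEs: overall, Grade 3/4 and drug-related summaries, and listings of SAEs, Grade 3/4 AEs and AEs leading to discontinuation. Section 12.4 tabulates response levels in the Efficacy Population, and there "no formal hypothesis testing will be performed for efficacy parameters".

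**The concern.** Safety is a primary objective in both phases (Sections 2.1.1 and 2.1.2). Phase 2 enrolls patients who were intolerant of, refractory to, or relapsed from an earlier JAK2 inhibitor. Section 1.2.1 itself refers to myelofibrosis progressing to acute myelogenous leukemia. Transformation and death are among the gravest outcomes in this population, and the plan routes them away from safety recording whenever the investigator calls them progression. That call is made in an open-label study.

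The main loss is the causality assessment. Section 8.1.3.3 requires one for each AE, so an event that never becomes an AE never receives one. Whether the drug contributed is then settled by definition and not by judgment of the case. The toxicology summary gives some reason not to do this: "NS-018 increased the incidence of micronucleated immature erythrocytes" in a rat assay, and numerical chromosome aberration was seen in vitro. Those results are not one-sided, as set out under the objection.

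**Working it through.** **1. Follow one event through the plan.** A patient meets the transformation criterion, and the investigator records only progression.

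- AE? No: Section 8.1.2 excludes it.
- Causality? None: Section 8.1.3.3 applies to AEs.
- SAE, if fatal? No: the death criterion in 8.1.3.1 applies only to an event that is already an AE. Grade 5 and the 24-hour report fail for the same reason.
- Line in a 12.5 event table or listing? No: all are AE-based, and Section 12.5 has no separate output for deaths or transformations.

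**2. Look for the event elsewhere.**

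- *Response table (12.4).* The event can appear as progressive disease, pooled with spleen growth.
- *Who is in that table (12.2.4).* Only patients with a post-baseline efficacy assessment. Formal response is first assessed at Cycle 2 Day 1. If palpation counts as an efficacy assessment, the first is at Cycle 1 Day 8 (Phase 1) or Day 15 (Phase 2). A patient who dies of progression before that point is in neither the response table nor the AE data.
- *Laboratory tables.* Hematology is kept, but the panel in Appendix G lists no blast count.
- *Earlier analyses (Section 12).* The Phase 1 interim and the Phase 2 six-month analysis cover pharmacokinetic, pharmacodynamic and safety data. Progression is classed as efficacy, so it lies outside both as described.
- *Follow-up (5.1.10, 5.2.12).* Only unresolved AEs are followed. No survival follow-up is described.

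**3. Reproduce the plan's figure.** Section 12.1 gives the chance of at least one event in N = 20, which is 1 − (1 − p)^20:

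| True rate p | Computed | Plan |
|---|---|---|
| 5% | 64.15% | 64.2% |
| 10% | 87.84% | 87.8% |
| 15% | 96.12% | 96.1% |
| 20% | 98.85% | 98.8% |
| 30% | 99.92% | > 99.9% |

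The table is correct. As a statement about AEs, it assumes that an event which occurs is recorded as one.

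**4. Illustrate the size.** The documents give no transformation rate, so the rates here are assumptions. Both phases together are 24 + 20 = 44 patients.

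| Assumed rate | At least one case, N = 20 | At least one case, N = 44 |
|---|---|---|
| 2% | 1 − 0.98^20 = 33% | 1 − 0.98^44 = 59% |
| 5% | 64% | 1 − 0.95^44 = 90% |
| 10% | 88% | 1 − 0.90^44 = 99% |

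Suppose 2 of 20 patients transformed and both were handled as progression. The AE data would show 0/20, with an exact 95% interval from 0 to 1 − 0.025^(1/20) = 16.8%. The true count of 2/20 has an exact interval of 1.2% to 31.7%. The zero comes from the recording rule and carries no information about the drug.

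**The case against.** A reader might infer that leukemia and progression deaths vanish from all safety data. The documents do not support that. Section 12.5 keeps laboratory values, shift tables, vital signs and ECGs for the whole Safety Population. An infection, bleed or cytopenia judged separate from progression remains an AE, and if fatal it is an SAE. Leukemia that does not meet the progression criteria could also still be recorded as an AE. Nor is the event lost to the whole trial, because progressive disease is tabulated by dose level and visit, with response assessed through End of Study.

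A reader might also infer that the rule is what disables the Phase 2 committee trigger. That trigger is a DLT-equivalent AE, and Section 6.1.1.2 already limits a DLT to events unrelated to the underlying disease. A transformation attributed to the disease would not trigger a meeting even if recorded as an AE. The committee's review after 10 patients covers pooled safety information more generally.

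The genotoxicity results do not show a leukemia risk either. The same section reports no gene mutations, no structural chromosome aberration and a negative rat comet assay. The picture is mixed, and the recording gap does not depend on it.

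Two further points have some force. Section 12 defers detail to a Statistical Analysis Plan and allows additional analyses, so the missing death and transformation outputs are shown for Section 12 only. Section 8.2 also obliges the sponsor to report potentially serious risks from any source. But an analysis plan cannot supply a causality assessment that was never collected, and the sponsor's duty depends on information this rule keeps out of the SAE stream. The broad AE definition in 8.1.2 does pull the other way, but the specific exclusion governs. If sites read it differently, recording will be inconsistent.

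**Conclusion.** The point holds in a bounded form. For a transformation or death attributed only to progression, the text leads to no AE, no causality assessment, no SAE report and no line in the Section 12.5 event outputs. What remains is at most a progressive-disease response that does not distinguish leukemia from spleen growth, or nothing if death precedes any post-baseline efficacy assessment.

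This rests on three conditions: sites apply the 8.1.2 exclusion as written, the event meets the progression criteria, and no separate complication is recorded. The probabilities above depend on assumed rates and are illustrations, not estimates. The structural finding does not depend on them.

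It should be fixed. It does not invalidate the design: no figure in the plan is wrong, and much of the safety data is unaffected. But with safety a primary objective, the two outcomes should be visible and assessed for causality.

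**What to change.** **Section 8.1.2.** Limit the exemption to progression by spleen criteria only, with no exemption for blood counts or blasts. An exemption for blood-count progression would be a mistake. Appendix I deliberately leaves cytopenia out of progression because it is hard to separate from drug-induced myelosuppression, and such wording could exempt hematologic toxicity or blast-defined progression. State that leukemic transformation, whether by marrow or peripheral blasts, and every death from first dose to 30 days after last dose are recorded and reported as AE/SAE with a causality assessment, whatever the attributed cause. The 30 days match the existing SAE window in Section 8.2.

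**Section 12.5.** Add a Safety Population listing and count by dose level of all deaths (with cause) and all leukemic transformations. Keep progressive disease in the response table as planned.

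**Cost.** A short text change, one table with its listing, and a few extra SAE reports. No visit, sample or patient is added. Section 6.1.1 marks the once-daily cohorts as completed, so sites would need to look back for deaths and transformations in those patients.

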**8.1.3 Assessment of Adverse Events**

Each AE will be assessed by the investigator with regard to the following categories.

#### 8.1.3.1 Seriousness

A serious AE (SAE) is defined as an AE that meets **any** of the following criteria:

- Results in death;
- Is life-threatening;

NOTE: The term “life-threatening” in the definition of “serious” refers to an event in which the patient was at risk of death at the time of the event. It does not refer to an event, which hypothetically might have caused death, if it were more severe.

- Requires hospitalization or prolongation of existing hospitalization;  
NOTE: In general, hospitalization for treatment of a pre-existing condition(s) that did not worsen from baseline is not considered an AE and should not be reported as an SAE.
- Results in disability/incapacity;
- Is a congenital anomaly/birth defect; or
- Is an important medical event.

NOTE: Important medical events that may not result in death, be life-threatening, or require hospitalization may be considered SAEs when, based upon appropriate medical judgment, they may jeopardize the patient and may require medical or surgical intervention to prevent one of the outcomes listed above. Examples of such medical events include allergic bronchospasm requiring intensive treatment in an emergency room or at home, blood dyscrasias or convulsions that do not result in inpatient hospitalizations, or the development of drug dependency.

#### 8.1.3.2 Intensity

Investigators should assess the severity of AEs according to CTCAE (see Appendix H). In general, CTCAE v4.0 Severity Grades are:

Grade 1:	Mild; asymptomatic or mild symptoms; clinical or diagnostic observations only; intervention not indicated;
Grade 2:	Moderate; minimal, local or noninvasive intervention indicated;
Grade 3:	Severe or medically significant but not immediately life-threatening; hospitalization or prolongation of hospitalization indicated; disabling; limiting self-care;
Grade 4:	Life-threatening consequences; urgent intervention indicated;
Grade 5:	Death related to AE.

#### 8.1.3.3 Causality

The causal relationship of the AE to study drug will be described as follows:

- Probable: the AE:
  - Follows a reasonable temporal sequence from administration of the study drug.
  - Could not be reasonably explained by the patient’s clinical state, environmental or toxic factors or other therapies administrated to the patient.
  - Disappears or decreases on cessation or reduction in dose of the study drug.

- Follows a known pattern of response to the study drug.
- Reappears or worsens upon rechallenge.
- Possible: the AE:
  - Follows a reasonable temporal sequence from administration of the study drug.
  - Could be reasonably explained by the patient's clinical state, environmental or toxic factors or other therapies administrated to the patient.
  - Follows a known pattern of response to the study drug.
- Unlikely: the AE
  - Does not follow a reasonable temporal sequence from administration of the study drug.
  - Could be reasonably explained by the patient's clinical state, environmental or toxic factors or other therapies administrated to the patient.
  - Does not follow a known pattern of response to the study drug.
  - Does not reappear or worsen upon rechallenge.
- Not related:
  - The AE does not meet the above criteria.
  - There is sufficient information that the etiology of the AE is not related to the study drug.

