While NS-018 was determined to be metabolized by CYP3A4 and CYP2D6 from the study using the human P450-expressing microsomes, CYP3A4 was considered to be mainly involved in the metabolism of NS-018 from the result of the chemical inhibition study. In the investigation of inhibitory effects on the metabolism of NS-018 after addition of specific inhibitors of each P450 isoform to human liver microsomes, only ketoconazole (an inhibitor of CYP3A4) inhibited the formation of metabolites and the disappearance of NS-018. The percentage of inhibition on the disappearance of NS-018 was 53.6% for CYP3A4. Therefore, the use of concomitant medications known to be strong inhibitors or inducers of CYP3A4 should be cautioned as described in Section 4.2.

The starting dose of NS-018 was selected based on the results of 4-week repeated dose, daily administration, oral gavage toxicity studies conducted in rats and dogs. The STD10 of rats was 150 mg/kg (estimated human equivalent dose was 24.2 mg/kg) and the HNSTD in dogs was 50 mg/kg (the estimated human equivalent dose was 27.8 mg/kg). Taking into account the human equivalent dose of 1/10 of the STD10 of rats and 1/6 of the HNSTD in dogs, the starting dose in this first-in-human study was determined to be 75 mg.

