Should BID dosing commence during the Phase I portion of the study, the SRC will meet after the last patient in that cohort has completed 28 days of dosing to assess the safety of that dosing schedule. Should the BID cohort be declared safe, the next BID cohort may begin. However, during the Phase 1 escalation portion of study, intrapatient schedule changes are not permitted (i.e., patients who start QD dosing regimen must remain on QD dosing and patients who start on BID dosing must remain on BID dosing).

If DLTs are seen in the 75 mg cohort, a cohort, labeled -1 and dosed at 50 mg, may be considered by the Safety Review Committee. Cohorts at doses >400 mg BID(800 mg/day) may be considered by the Sponsor if agreed by the Safety Review Committee after review of PK, PD, and safety data. The maximum planned increase in dose between cohorts will be 200 mg as the total daily dose (e.g., the dose level above 400 mg BID will not exceed 500 mg BID).

Once a cohort is declared safe, patients treated at lower doses in earlier cohorts can be considered for intrapatient dose escalation. Intrapatient dose escalation is permissible in individual patients if the patient has received at least 3 months of study drug at a given dose and has not experienced any Grade 3 or 4 drug-related toxicity and no evidence of significant clinical efficacy and the next highest dose cohort has already been declared safe by the Safety Review Committee. Intrapatient dose escalation depends on the total daily dose and the confirmation of safety based on QD and/or BID dose regimen at a dose level. For example a patient at 100mg BID can increase by up to 200 mg BID only when 200 mg BID is declared safe by the Safety Review Committee. In the event that intrapatient dose escalation would result in a patient escalating more than one dose at a time, the eligibility of the patient for dose escalation would be reviewed and the dose level determined by the investigator and the medical monitor.

After intrapatient dose escalation, patients will return to the study site after 1 month of treatment at the higher dose to undergo physical examination (including assessment of spleen size by palpation) and safety laboratory tests (hematology and chemistry). Patients will return to 3-month visit schedule after this visit.

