**12.5 Safety Analyses**

All safety analyses will be based on the Safety Population. Adverse events, vital sign measurements, clinical laboratory information, ECG measurements, and concomitant medications will be summarized by dose level.

Adverse events will be coded using the Medical Dictionary for Regulatory Activities (MedDRA) classification system. The severity of all AEs will be graded according to the NCI CTEP CTCAE version 4.0. A summary of all AEs will be provided by system organ class and preferred term. The same summaries will be performed for Grade 3/4 AEs and drug-related AEs. Listings will be presented for SAEs, Grade 3/4 AEs, and AEs leading to discontinuation from the study.

Clinical laboratory evaluations at each visit and change from baseline (Cycle 1 Day 1) will be summarized by dose level. A laboratory value shift table will be provided. Vital signs and ECG parameters at each assessment time will be summarized by dose level. Other safety variables and their changes from baseline (when applicable) will be summarized by dose level at each of the scheduled assessment times.

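### The causality scale in section 8.1.3.3 has no place under Probable, Possible or Unlikely for a plausibly timed event with no known pattern, and drug-related is never tied to its categories

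*Combined protocol and SAP*

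**What the plan says.** Section 8.1.3.3 has four causality categories, each with a bullet list.

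- **Probable** has five bullets: plausible timing, no other reasonable explanation, improvement on stopping or reducing the drug, "Follows a known pattern of response to the study drug", and recurrence or worsening on rechallenge. The rechallenge bullet carries no qualifier for cases where none was done.
- **Possible** has three: plausible timing, another reasonable explanation, and the same known-pattern bullet.
- **Unlikely** has four: "Does not follow a reasonable temporal sequence from administration of the study drug", another reasonable explanation, "Does not follow a known pattern of response to the study drug", and no recurrence on rechallenge.
- **Not related** has two: "The AE does not meet the above criteria" and "There is sufficient information that the etiology of the AE is not related to the study drug".

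No rule says whether the bullets in a list are joined by *and* or by *or*. Section 8.1.3.1 (Seriousness), by contrast, says outright that one criterion is enough.

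Section 1.2.2 describes the setting: "the starting dose in this first-in-human study was determined to be 75 mg".

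Relatedness is then used in several places. Section 12.5 says "The same summaries will be performed for Grade 3/4 AEs and drug-related AEs" but names no causality categories. Section 6.1.1 allows intrapatient escalation only if, among other conditions, the patient "has not experienced any Grade 3 or 4 drug-related toxicity"; a similar condition governs the move from a Phase 1 dose to the Phase 2 dose. The restart wording in section 6.1.1.1 refers to drug-related toxicity. Under section 8.2, SAEs more than 30 days after the last dose are reported only if the investigator considers them related.

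**The concern.** Early in a drug's clinical use, many true toxicities have no established human pattern. A scale that lists a known pattern under both of its positive categories, and the lack of one under Unlikely, counts novelty against causality. Safety is a primary objective in both phases, so attribution should be able to register a new toxicity.

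The rechallenge bullet adds a second problem, which also affects known toxicities. After the gravest events rechallenge will often not take place: section 6.1.1.1 bars further treatment after life-threatening Grade 4 non-hematological toxicity unless the Safety Review Committee reviews the case.

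At stake are the drug-related AE summaries, the consistency of attribution between sites, and the passages of sections 6.1.1, 6.1.1.1 and 8.2 that use relatedness.

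**Working it through.** The plan gives no figure to reproduce here; the check is one of logic.

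**Inputs.** The section 8.1.3.3 bullets use five yes/no attributes: T (plausible timing), A (another reasonable explanation), D (positive dechallenge), K (known pattern) and R (positive rechallenge). A rechallenge or dechallenge that was not done is coded as not positive. There are 2^5 = 32 profiles. These are logical combinations, not expected frequencies of events.

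**Reading 1: all bullets in a list must be met.**

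- Probable = T, not A, D, K, R: 1 profile.
- Possible = T, A, K, with D and R free: 2 × 2 = 4 profiles.
- Unlikely = not T, A, not K, not R, with D free: 2 profiles.
- None of the three: 32 − 1 − 4 − 2 = 25 profiles.

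| Subset | Profiles | Probable | Possible | Unlikely | None of the three |
|---|---|---|---|---|---|
| No known pattern | 16 | 0 | 0 | 2 | 14 |
| No known pattern, plausible timing | 8 | 0 | 0 | 0 | 8 |
| Known pattern | 16 | 1 | 4 | 0 | 11 |

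The second row includes the strongest causal case that a new toxicity can present: plausible timing, no other explanation, positive dechallenge and positive rechallenge.

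The third row shows that the defect goes beyond new toxicities. An event with known pattern, plausible timing, no other explanation and positive dechallenge, but no rechallenge, fails Probable for want of rechallenge and Possible for want of another explanation.

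Where the unplaced events go depends on Not related. If its first bullet is enough alone, they become Not related. If both bullets are needed, an event without positive evidence of another cause has no category.

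**Reading 2: any one bullet is enough.**

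- Probable fails only for not T, A, not D, not K, not R: 1 profile.
- Possible fails only for not T, not A, not K: 4 profiles.
- Unlikely fails only for T, not A, K, R: 2 profiles.

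These sets do not overlap, so 32 − 1 − 4 − 2 = 25 profiles meet all three categories and the other 7 meet two. No profile has a unique category.

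**Would deleting the known-pattern bullet be enough?** Under Reading 1, of the 8 profiles with plausible timing and no known pattern, 1 becomes Probable (not A, D, R) and 4 become Possible (A, with D and R free). The other 8 − 5 = 3 have no other explanation and lack a positive dechallenge, a positive rechallenge, or both. They remain unplaced, so deletion alone does not suffice.

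**Effect on counts.** Suppose drug-related means Probable or Possible, and let f be the share of truly drug-caused events with no known pattern. Under Reading 1 all of these are lost, so the shortfall is at least f. The documents give no value for f, and nothing in them narrows it within 0 to 1.

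**The case against.** The strongest reply is that the bullets are features for the investigator to weigh, not a checklist. A strict conjunction would bar Probable for every event without rechallenge, typical known toxicities included, so the authors probably did not intend one. This has force as a guess about practice. But section 8.1.3.3 does not say it, it leaves sites free to differ, and even a weighing approach counts the lack of a known pattern against causality.

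A second reply is that patterns are not wholly unknown. Section 1.2.1 reports hematological, renal and gastrointestinal findings in animals, and the dose table in section 6.1.1 marks the once-daily cohorts as completed. This narrows the group of affected events, but a toxicity not yet seen remains excluded.

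Three stronger readings are tempting, and the documents do not support them.

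- **Every event without a known pattern defaults to Not related.** This needs the first Not related bullet to suffice alone while the other lists are read cumulatively. If both bullets are required, such an event has no category unless there is positive evidence of another cause. Unlikely also takes 2 of the 16 no-pattern profiles.
- **Dose finding is distorted.** Section 6.1.1.2 attributes DLTs by its own wording, and the MTD rule in section 6.1.1.3 counts those DLTs. The Safety Review Committee may also treat other important events as DLTs. Neither section uses this scale.
- **New toxicities disappear from the report, or the loss can be given as a percentage.** The all-AE and Grade 3/4 summaries, the listings of SAEs and of AEs leading to discontinuation, and SAE reporting up to 30 days after the last dose do not depend on the scale. No percentage can be derived.

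It is also fair to say that, with drug-related undefined, any loss from the drug-related counts is conditional. Section 12 leaves the description of the analyses to a Statistical Analysis Plan, and the text available for review does not define the term.

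**Conclusion.** The point stands as a drafting defect with a bounded effect. Read cumulatively, which the contrast with section 8.1.3.1 makes the more natural reading, section 8.1.3.3 leaves 8 of 8 profiles with plausible timing and no known pattern outside Probable, Possible and Unlikely. It also leaves outside Probable and Possible a known-pattern event with no other explanation and no rechallenge. Read as any-criterion, the scale does not classify.

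The step to an undercount in the drug-related AE summary rests on two assumptions: that the bullets are applied literally, and that drug-related means Probable or Possible. The relatedness wording in sections 6.1.1 and 6.1.1.1, and for late SAEs in section 8.2, is exposed in the same way. The change should be made, but no dose-finding conclusion depends on it.

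**What to change.** In section 8.1.3.3:

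- Make known pattern and rechallenge (if performed) supportive, not required.
- Define Probable as plausible timing with no other reasonable explanation.
- Define Possible as plausible timing with another reasonable explanation.
- Keep Unlikely for implausible timing with another reasonable explanation.
- Restrict Not related to positive evidence of another cause.

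On timing and alternative explanation alone, Probable, Possible and Unlikely then take 8 profiles each, so 24 of the 32 have exactly one of these categories. The remaining 8 (implausible timing, no other explanation) still need one, and the sponsor should name it in the same edit.

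In section 12.5, state which categories count as drug-related for the summaries. The sponsor should reconcile the use of the term in sections 6.1.1 and 6.1.1.1 with that definition; this review does not set the threshold for escalation or restart.

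The direct cost is a rewording of one subsection, a sentence in section 12.5 and matching eCRF guidance. The drug-related AE rate will look somewhat higher. Because the once-daily cohorts are completed, attributions made before and after the change will not be directly comparable and should be flagged or re-reviewed.
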